### 7.4 Per-Protocol (PP) Population Analysis Set

*The PP Population is a subset of the modified Intent-to-Treat Population and will include patients without major protocol deviations.*

Major deviations shall include:

- Deviation from an IEC/IRB approved protocol which compromise the safety and welfare of participating subjects or compromise the integrity of the study and /or the completeness, accuracy and reliability of study data. Examples of deviations included but not limited to:
  - o Failure to obtain informed consent from the enrolled subject (e.g., there is no documentation of informed consent);
  - o Informed consent is obtained after initiation of study procedure;
  - o Enrollment of subject who has failed to meet the eligibility criteria.

The list of protocol deviations with categorization with respect to major and minor deviations will be generated prior to the study database lock. Sponsor's Medical monitor will review all deviations prior to database lock and decide whether to include the patient in a PP analysis population set. The PP population analysis set will also be used for efficacy assessment.

**Note:** If the patients qualifying for mITT set are same as the patients qualifying for PP set, the respective tables and figures proposed using PP set will not be produced to avoid the duplication of the results.

*Membership in the analysis populations will be determined before database lock.*

## **8. Randomization and Blinding**

*This is a non-randomized, open label study.*

## **9. Method of Analysis**

### **9.1 Statistical Hypotheses**

There are no formal statistical hypotheses tested in this study.

### **9.2 Interim Analysis**

No formal interim analysis is planned for this study.

### **9.3 Handling of Missing Data**

#### **9.3.1 Missing Dates for Adverse Events and Concomitant Medications**

Missing dates (either completely or partially) of adverse events and concomitant medications will be imputed as explained below for the purposes of calculation of durations.

#### **For end of concomitant medications or adverse events:**

- **If only Day of end date is missing:**  
The last date of the month and year reported or the date of the final contact with the subject, whichever is earlier, will be used as the end date.
- **If Day and Month of end date are missing:**  
The last date of year i.e. December 31 of the year reported or the date of the last study contact with the subject, whichever is earlier, will be used as the end date.
- **If Year of end date or complete end date is missing:**  
If the year of end of medication/event is missing or end date is completely missing, then no end date will be imputed.

#### **For the start of a concomitant medication or adverse event:**

- **If only Day of start date is missing:**
  - If the start year and month of medication/event are the same as that for the first dose date, then following approach will be used:
    - If the end date of medication/event is NOT before the first dose date or end date of medication/event is completely missing, then impute the start day as the day of first dose date.
    - Otherwise, impute the start day as 1.

- If the start year and month of medication/event are NOT same as that for the first dose date, then
  - Impute the start day as 1.
- **If Day and Month of start date are missing:**
  - If start year of medication/event is same as first dose year, then following approach will be used:
    - i. For medication, impute the start Month as January and the Day as 1
    - ii. For adverse event,
  - If the end date of event is NOT before the first dose date or end date of event is completely missing, then impute the start Month and Day as the Month and Day of first dose date;
  - Otherwise, impute the start Month as January and the Day as 1.
- If start year of medication/event is NOT same as first dose year, then
  - Impute start Month as January and the Day as 1.

- **If Year of start date or complete start date is missing:**

If the year of start of medication/event is missing or start date is completely missing, then no start date will be imputed.

### **9.3.2 Missing Dates for Efficacy Endpoints**

For time-to-event endpoints (Objective Response Rate and Duration of Response), if the last objective response date is completely missing, no imputation will be performed.

However, the incomplete/partial dates will be handled following the general conventions as detailed in Section [9.3.1](#).

### **9.3.3 Missing dates for Primary Diagnosis/Prior therapy**

Partial primary diagnosis and prior therapy dates will have imputation performed as explained below for the purposes of calculation of relativity to study medication.

- If only Day is missing, impute the day 1
- If Day and Month are missing, impute the Month as January and the Day as 1.
- If the year of primary diagnosis is missing or the date of primary diagnosis is completely missing, then no date will be imputed.

## **10. Statistical Analysis**

*Unless otherwise stated, all statistical analyses will be performed using a two-sided hypothesis test at the overall 5% level of significance.*

*Data will be displayed in all listings sorted by phase, group and patient number. When count data are presented, the percentage will be suppressed when the count is zero in order to draw attention to the non-zero counts. A row denoted “Missing” will be included in count tabulations where necessary to account for dropouts and missing values. Unless otherwise specified, the denominator for percentages will be the number of patients with a non-missing assessment in a given treatment group within the analysis population of interest.*

All the patient data including, demographics, medical history, prior/concomitant medications, safety data (where appropriate) and efficacy data will be summarized by following two modes of representation:

1. Dose Escalation (Cohort 1, Cohort 2, Cohort 3, All Cohorts), Dose Expansion (Group 1, Group 2, Both Groups) and Overall.
2. PTCL, CTCL and Overall

All statistical analyses will be performed using SAS 9.4 or higher.

### **10.1 Patient Disposition**

A tabular presentation of the patient disposition will be provided. It will include the number of patients screened, enrolled, dosed, completed the treatment, as well as the number of dropouts, with reasons for dropouts, number in each population sets, number of patients with dose reduction, drug interruptions (transient discontinuation) and dose discontinuation (permanent discontinuation) etc. All patients' data will be used for this analysis. This data will also be listed.

### **10.2 Demographic and Baseline Characteristics**

Analysis set: Safety

Demographic and baseline characteristics data will be summarized using descriptive statistics (n, mean, standard deviation, median, minimum, and maximum) for continuous variables, and using frequencies and percentages for categorical variables.

Demographic characteristics will include age, race, gender, height, etc.

Disease characteristics will include time from initial diagnosis to treatment, subtype of PTCL, subtype of CTCL, staging at screening, number of prior therapies, number of subject relapsed or refractory to the last therapy, time from date of last therapy to study treatment, ECOG performance status at screening, etc.

### **10.3 Medical and Surgical History**

Analysis set: Safety

This data will be summarized using frequencies and percentages by System Organ Class and Preferred Term. A listing will also be provided.

The medical history data will be coded using MedDRA dictionary [Version 24.0].

## 10.4 Prior and Concomitant Medications

Analysis set: Safety

Concomitant medications are those that were taken while on study drug. Also, the medications / non-drug treatments which start after study treatment will be termed as 'Concomitant'.

Prior medications are those that were taken prior to the first dose of study drug.

The medication data will be coded using WHO-Drug dictionary (WHODRUG GLOBAL B3 March, 2021) and the non-drug treatments data will be coded using MedDRA dictionary [Version 24.0].

A summary of frequencies and percentages by ATC level 2 and Preferred Terms and the listing of the prior and concomitant treatments taken will be provided.

## 10.5 Efficacy Analysis

Analysis Set: mITT and PP

All the efficacy analyses will be based on the data collected in the Dose escalation and Dose Expansion Phase of the study.

Note: The analyses outlined below are subject to availability of adequate data.

### 10.5.1 Objective Response Rate (ORR)

It is *defined as sum of CR and PR rates, assessed according to the Lugano Classification for initial evaluation, staging, and response assessment of Hodgkin/non-Hodgkin lymphoma in PTCL patients; and according to the modified Severity Weighted Assessment Tool (mSWAT) in CTCL patients.*

Additionally, Disease Control Rate (DCR= CR+PR+SD) will be presented.

This data will be summarized using frequency, and percentage and the 95% CI (Using exact method based on binomial distribution, subject to availability of adequate data). The corresponding listing will also be provided.

Also, the Conversion rate, defined as the conversion from partial response (PR) to CR or from SD to PR/CR that occurs during the first 7 months of treatment (till Cycle 8 Day 1) will be summarized for the Overall group of patients using frequency, percentage and the 95% CI (Using exact method based on binomial distribution, subject to availability of adequate data). This data will not be listed.

$$\text{Conversion Rate} = \frac{\text{Total number of conversions} * 100}{\text{SD or PR at the first efficacy assessment}}$$

Note: First efficacy assessment = Cycle 3 Day 1.

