6.6 Bone Marrow Biopsy

- **PTCL:**

A bone marrow biopsy and/or aspirate should be collected ≤ 3 months prior to C1D1 and/or to confirm a complete response to the study drug. If patient has negative bone marrow at baseline, there is no need to have it repeated to confirm CR. Additional biopsy will be obtained if clinically indicated.

- **CTCL patients with predominantly blood involvement (B₂):**

Patients with predominantly blood involvement (B₂) will have a bone marrow biopsy at screening (unless it has been shown to be negative within the last 6 months) and as indicated to confirm a complete response.

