6.7 Radiological Evaluations

Initial disease assessment by tumor imaging (baseline scan) must be performed within 28 days prior to C1D1. The site investigator/designee must review radiological images to confirm the subject has measurable disease as defined in the inclusion criteria. Disease assessments or scans performed as part of routine clinical management are acceptable for use as the screening scan if they are of diagnostic quality and performed within 28 days prior to the first dose of trial treatment.

- **PTCL and CTCL patients with lymph node/visceral involvement:**

Computed tomography (CT) scan (chest/abdomen/pelvis/neck as appropriate) will be performed at screening for disease assessment. PET-CT is preferred for FDG-avid lymphomas. Other radiological evaluations (e.g. X-ray/MRI/USG) will be performed if warranted.

- **CTCL patients with skin and blood involvement:**

CT scan will be performed at screening for disease assessment.

- In patients with clinically early disease (maximum/current $T_{1-2}N_0M_0B_{0-1}$), repeat scans should not be performed except in cases of an objective response (OR) in the skin.
- In those patients with more advanced disease at baseline ($TNMB > T_{1-2}N_0M_0B_{0-1}$), CT scan should be performed at the time of PR and CR in the skin; any time there is a question of new or PD in the lymph nodes or viscera; and at end of study.

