6.8 Skin Biopsy

In CTCL patients, skin biopsy should be taken at screening, and to confirm a complete response. Biopsy should be performed at the most indurated area if only one biopsy. Skin biopsy will not be done in other patients.

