15. A bone marrow biopsy: PTCL: Bone marrow biopsy should be collected \leq 12 weeks prior to C1D1 and/or to confirm a complete response to the study drug. If patient has negative bone marrow at baseline, there is no need to have it repeated to confirm CR. Additional biopsy will be obtained if clinically indicated. CTCL patients with predominantly blood involvement (B₂) will have a bone marrow biopsy at screening (unless it has been shown to be negative within the last 6 months) and as indicated to confirm a complete response.
16. Skin biopsy: In CTCL patients, skin biopsy should be performed at screening, and to confirm a complete response. Historical data of 12 weeks is acceptable.
17. Radiological scan: In PTCL and CTCL patients with nodal and visceral involvement, PET and “diagnostic quality” CT scan will be performed at the time of screening within 28 days of screening. Following screening, CT scans should be repeated at C3D1 (\pm 7 days), C5D1 (\pm 7 days) and C8D1 (\pm 7 days). PET should be done at C3D1 (\pm 7 days) and to confirm CR.
18. Skin assessment: In all CTCL patients, mSWAT will be performed at the time of screening within 28 days of screening and at C3D1 (\pm 7 days), C5D1 (\pm 7 days) and C8D1 (\pm 7 days). Disease response assessment will be performed at C3D1 (\pm 7 days), C5D1 (\pm 7 days) and C8D1 (\pm 7 days) and/ or at the EOT or as clinically indicated using mSWAT.
19. Skin photograph: In CTCL patients, skin lesion photograph will be taken at screening, at the time of response (PR/CR/PD) and at other time points as required by the PI.
20. Blood will be collected for biomarkers (e.g. sIL2R and CTACK for PTCL; CD30, IL-31 and IL-32 for CTCL).
21. Tenalisib will be administered orally twice a day from Day 3 (C1D3) onward in 28-days of cycle for 7 cycles in absence of disease progression or toxicity warranting discontinuation of therapy. On the day of Romidepsin administration, the morning dose of Tenalisib should be given in clinic one hour prior to Romidepsin infusion. Tenalisib will be dispensed at the start of each cycle (C1D1, C2D1, C3D1 ...). Only in Cycle 1, Tenalisib will be

given starting from Day 3 (i.e. C1D3). Patients will be, therefore, be instructed to start the treatment on C1D3 and will be informed that they will receive Tenalisib for 25 days in the first cycle.

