8.2 Response Evaluations and Measurements

In all patients (PTCL and CTCL), the response will be assessed approximately at 8 weeks interval for the first two assessments [(e.g. C3D1 (\pm 7 days), C5D1 (\pm 7 days)] and then at C8D1 (\pm 7 days) and/ or at the EOT or as clinically indicated (if clinical progression is suspected).

- **PTCL**

PTCL patients will be evaluated according to Lugano classification Cheson 2014)^[16] ([Appendix C](#)) using the CT scan. PET-CT will be preferred for FDG-avid lymphomas. The modality chosen should be the same throughout the duration of the study. In addition, PET-CT will be performed at C3D1 (\pm 7 days) and to confirm CR. If PET and CT scan at Screening are negative for disease involvement in the neck, subsequent CT scans may not include neck. If PET and CT scans at Screening are positive for disease involvement of the neck, subsequent CT scans must include neck. Disease assessments and imaging should not be delayed for delays in cycle starts. Disease assessments and imaging should be continued until documented disease progression, the start of new anti-cancer treatment, withdrawal of consent, death, or the end of the study, whichever occurs first.

Each participating site will be responsible for radiological review and confirmation of response as per standard efficacy guidelines. The frequency outlined is the minimum required for study participation. Patients who progress according to the corresponding criteria will receive no further treatment. Patients who respond to the treatment (i.e., CR, PR or SD) may remain on trial. All disease specific assessments are to be completed as applicable to disease type.

- **CTCL:**

CTCL patients will be evaluated as per modified Severity Weighted Assessment Tool (mSWAT) ([Appendix F](#)).^[17] Additionally, CT scan will be done in the CTCL patients with lymph node and visceral involvement. CTCL patients with subcutaneous lesions which cannot be measured by mSWAT will be assessed by change in PET-CT avid lesions. Bone marrow biopsy will be performed in patients with B2 blood involvement. In these patients, Sezary cell count will be quantified by flow cytometry or morphology in blood/bone marrow.

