Appendix F: Modified Severity Weighted Assessment Tool (mSWAT)

Body Region	% BSA in Body Region	Assessment of Involvement in Patient's Skin		
		Patch*	Plaque†	Tumor‡
Head	7			
Neck	2			
Anterior trunk	13			
Arms	8			
Forearms	6			
Hands	5			
Posterior trunk	13			
Buttocks	5			
Thighs	19			
Legs	14			
Feet	7			
Groin	1			
Subtotal of lesion BSA				
Weighting factor		×1	×2	×4
Subtotal lesion BSA × weighting factor				

- NOTE. mSWAT score equals summation of each column line.
- Abbreviations: BSA, body surface area; mSWAT, modified Severity Weighted Assessment Tool.
- \triangle^* Any size lesion without induration or significant elevation above the surrounding uninvolved skin; poikiloderma may be present.
- $\triangle^†$ Any size lesion that is elevated or indurated; crusting, ulceration, or poikiloderma may be present.
- $\triangle^‡$ Any solid or nodular lesion ≥ 1 cm in diameter with evidence of deep infiltration in the skin and/or vertical growth.

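### CTCL response is defined by a skin-only score, and neither document says how nodal, visceral, blood or PET-CT findings change the response call or end the duration of response

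*SAP*

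**What the plan says.** **Endpoint.** Protocol 3.1.2 and SAP 4.2 and 10.5.1 use the same sentence: Lugano in PTCL, "and according to the modified Severity Weighted Assessment Tool (mSWAT) in CTCL patients". The schedule footnotes (Table 5, footnote 18; Table 6, footnote 17) place CTCL response assessment at C3D1, C5D1, C8D1 and/or end of treatment, "or as clinically indicated using mSWAT". Appendix F is a body-region grid, and its only scoring instruction is that the "mSWAT score equals summation of each column line".

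**Other data collected in CTCL.** In disease more advanced than T1-2N0M0B0-1, protocol 6.7 says a "CT scan should be performed at the time of PR and CR in the skin", also when nodal or visceral progression is in question and at end of study. In early disease "repeat scans should not be performed except in cases of an objective response (OR) in the skin". Protocol 8.2 adds CT for nodal or visceral involvement and uses PET-CT change for subcutaneous lesions that mSWAT cannot measure. For patients with B2 blood involvement, the "Sezary cell count will be quantified by flow cytometry or morphology in blood/bone marrow".

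**Confirmation of CR.** Under 6.8, "skin biopsy should be taken at screening, and to confirm a complete response". Under 6.6, B2 patients have marrow at screening (unless recently negative) "and as indicated to confirm a complete response".

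**DoR.** SAP 10.5.2 runs from first response to documented progression and censors patients without progression at their last disease assessment. It plans a CTCL Kaplan-Meier display that pools escalation and expansion.

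**The concern.** CTCL can involve skin, nodes, viscera and blood, and the protocol collects data on all four. The endpoint uses one. If skin improves while another compartment progresses, the endpoint sentence gives a response and no other text overrides it.

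ORR, DCR, conversion rate and BOR all use the same response categories. DoR adds a second dependence: its event is progression, and for CTCL the documents do not say whether progression means skin, any compartment or the site's overall judgement. The same course could be an event at one site and a censored time at another. The protocol foresees about 15 centers, and response is investigator-assessed. A patient with both skin and nodal lesions may be placed in either disease group with the investigator's approval (note to protocol 4.1), which also decides which criteria apply.

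**Working it through.** There is no plan figure to reproduce: the 12 patients per group carry no formal calculation. The check is of the text, followed by the size of one reclassification.

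**1. What the stated CTCL rule measures.** The Appendix F regions add to 7 + 2 + 13 + 8 + 6 + 5 + 13 + 5 + 19 + 14 + 7 + 1 = 100% of body surface. With weights of 1, 2 and 4 the maximum score is 4 × 100 = 400. The sheet is sound as a skin score. Nothing outside the skin enters it. It gives no percentage change for PR, SD or PD and no baseline or nadir reference.

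**2. What the other data are said to do.**

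| Data | Where | Stated effect on the CTCL response call |
|---|---|---|
| Skin biopsy | 6.8 | Confirms CR; silent on PR, SD, PD |
| Marrow in B2 patients | 6.6 | Confirms CR; silent on PR, SD, PD |
| Nodal/visceral CT | 6.7, 8.2, schedule footnotes | Says when to scan; no consequence given |
| PET-CT, subcutaneous lesions | 8.2 | Method given; size of change not given |
| Sezary count | 8.2 | None; no row in Tables 5 and 6 |
| Non-target progression | 8.1 | To be noted; no consequence given for CTCL |

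**3. One course read literally.** A CTCL patient with nodal disease reaches PR on mSWAT, whatever cut-off is used. Section 6.7 calls for a CT, and it shows nodal progression.
- *ORR:* the endpoint sentence names mSWAT, so the patient is a responder. No other text withdraws the response.
- *DoR:* if nodal progression counts, the response starts and ends together, or never existed. If only skin counts, the time runs on to skin progression or to censoring at the last assessment. Neither document chooses.

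**4. Size of one reclassification.** Step = 100/n points.
- Expansion Group 2: n = 12, so 100/12 = 8.3 points.
- Pooled CTCL, in the extreme case that the stated maximum of 18 escalation patients were all CTCL: n = 12 + 18 = 30, so 100/30 = 3.3 points.

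SAP 10 and 10.5 call for efficacy by disease type and from both phases, so both denominators are relevant. The step is larger if mITT exclusions reduce n.

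Illustration in Group 2, with an assumed 5 responders and 0, 1 or 2 reclassified (exact binomial 95% CI):
- 5/12 = 41.7% (15.2 to 72.3)
- 4/12 = 33.3% (9.9 to 65.1)
- 3/12 = 25.0% (5.5 to 57.2)

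The first interval is 72.3 − 15.2 = 57.1 points wide, so sampling error exceeds the effect of one or two reclassified patients.

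**5. Secondary wording point.** Protocol 8.1 takes a baseline sum of single diameters (short axis for nodes) as the reference for regression. Appendix C uses SPD for PR and SD, LDi for CT-based CR, and PPD with LDi or SDi for PD. A node going from 4 × 2 to 2 × 2 cm has SPD 8 to 4 cm² (−50%, meeting the Appendix C size criterion for PR) and short axis 2 to 2 cm (0%).

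**The case against.** The strongest reply is that the criteria are incorporated by citation. Protocol 8.2 cites reference 17 in the sentence on how CTCL is evaluated, just as it cites reference 16 for PTCL, and the title of reference 17 covers end points and response criteria in mycosis fungoides and Sézary syndrome. In addition, 8.1 is not limited to PTCL: it asks for target lesions representing all involved organs and for unequivocal non-target progression to be noted. Protocol 7.4.8, on adverse-event reporting, treats new lesions as progression. SAP 14 lists an overall tumor assessment apart from the mSWAT assessment, and SAP 10.5.3 takes best response as confirmed by the site investigator. Sites may well record a call that goes beyond skin.

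Much of this stands, and it rules out three stronger readings that a reader might infer:
- *That CTCL progression has no definition at all.* A source is cited whose content cannot be checked here. What can be said is that its criteria are not written out or expressly adopted, whereas Lugano is reproduced in Appendix C, and that the SAP reference list omits it.
- *That skin responders with nodal progression will be counted.* The literal endpoint allows it; the separate overall assessment may prevent it. The documents do not say which entry feeds ORR for CTCL.
- *That one patient could settle a comparison with the single-agent CTCL rates in the protocol background.* No such comparison is planned, SAP 9.1 tests no hypothesis, and the pooled displays shrink the step.

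What the reply does not supply is a rule linking compartments to the response category, or to the event in the CTCL DoR curve.

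**Conclusion.** The point holds in this form: the CTCL endpoint is worded as a skin-only measure, extracutaneous data are collected without a stated effect on response or progression, and a literal reading can count a patient with documented extracutaneous progression as a responder. Missing mSWAT cut-offs alone would be missing detail; a skin-only rule that can give the wrong ORR and DoR goes further.

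Each reclassified patient is worth 8.3 points at n = 12 and about 3.3 at n = 30. How many would be affected cannot be known from the documents; the 5 responders and 0 to 2 reclassifications are assumptions, as is the all-CTCL escalation part behind n = 30. ORR and DoR are secondary and no hypothesis is tested, so no formal decision is at risk; what suffers is the interpretability of the activity estimate. It should be fixed.

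The sum of diameters in 8.1 is only an inconsistency: it has no threshold and is not a rival PR rule, and it matters only for CT-based measurement.

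**What to change.** In SAP 4.2, 10.5.1 and 10.5.2, and protocol 3.1.2:
- Define CTCL response for analysis as a global response: skin response by mSWAT under criteria that the sponsor names and expressly adopts, with no documented progression in involved nodes, viscera or blood on assessments already collected.
- For subcutaneous lesions, use PET-CT change where done, with its criterion stated.
- End DoR with the same progression event.
- State whether the overall tumor assessment is this global call, and how it is formed.
- Report skin-only mSWAT response as a separate line.
- Report how many responders had an involved compartment that was not reassessed.

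This concerns the analysis definition only. The sponsor should reconcile it with the progression criteria that protocol 8.2 refers to without naming.

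As a secondary edit, reconcile the sum of diameters in 8.1 with Appendix C, for example by recording baseline SPD over up to 6 target lesions.

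**Cost.** Wording, programming and a check that the eCRF holds Sezary counts and both perpendicular diameters. No new assessments are needed, which also sets the limits: no serial Sezary row in Tables 5 and 6, PET scheduled only at C3D1 and to confirm CR, and repeat CT restricted in early-stage CTCL. Some compartments will therefore not have been reassessed. CTCL ORR may be slightly lower than a skin-only rate and less comparable with skin-only reports; the separate skin line covers that.

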3.2 Design of Trial

This is a multi-center, open label, non-randomized, two-part Phase I/II study of Tenalisib in

combination with Romidepsin in adult patients with relapsed/refractory TCL. The first part is an open-label, 3+3 dose escalation, Phase I study for MTD determination. The second part is a Phase II, dose expansion to delineate the safety and anti-tumor activity of the combination at the MTD/optimal dose.

In dose escalation, a minimum of 2 and maximum 18 patients will be enrolled in three dose levels unless additional dose levels are required to reach MTD/ optimal dose. In dose expansion, up to 24 TCL patients will be enrolled (Group 1= 12 PTCL patients and Group 2= 12 CTCL patients).

The study will end when all ongoing subjects have reached their third tumor assessment on Cycle 8/Day 1 (C8D1) or have discontinued from the study for any reason, whichever is earlier. At the end of the study, all ongoing patients with no evident disease progression will be given the opportunity to enroll in an open-label compassionate use study protocol and will be followed up.

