9.4.3 Efficacy analyses

The efficacy endpoints will include:

- ORR: The percentages of CR, CR+PR, and CR+PR+SD as well as Conversion Rate for Group 2 will be presented, as will the median duration of response. The 95% confidence intervals of these percentages may also be presented.
- DOR: DOR is defined as time from the initial response to documented disease progression. This variable will be analyzed via Kaplan-Meier methodology.

Additional analyses may also be performed as appropriate.

These analyses will be performed from time to time for presentation/publication purposes.

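### The SAP's conversion rate has no once-per-patient rule, so any repeat conversions would inflate the rate and make its exact binomial interval inapplicable

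*SAP*

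**What the plan says.** SAP 10.5.1 describes a conversion as "defined as the conversion from partial response (PR) to CR or from SD to PR/CR", within a window that runs to C8D1. The displayed formula has "Total number of conversions", times 100, as numerator and "SD or PR at the first efficacy assessment" as denominator. A note fixes the time point: "First efficacy assessment = Cycle 3 Day 1". The rate "will be summarized for the Overall group of patients using frequency, percentage and the 95% CI", and that interval is to be exact, from the binomial distribution, if there are enough data. Conversion data are not to be listed.

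The protocol mentions the rate once, in 9.4.3, without defining it: "as well as Conversion Rate for Group 2 will be presented". Group 2 is the CTCL expansion group. SAP Section 10 says that efficacy data will be summarized in two layouts: by escalation cohort, expansion group (Group 1, Group 2, both) and overall; and by PTCL, CTCL and overall.

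Protocol 8.2 schedules response assessments at C3D1, C5D1 and C8D1, with others as clinically indicated.

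**The concern.** Read literally, the numerator counts events while the denominator counts patients, since each patient has a single status at C3D1. Two scheduled assessments follow C3D1, so SD at C3D1, PR at C5D1 and CR at C8D1 contains two qualifying steps in one denominator patient. Such deepening of response is what Protocol 1.3.2 hopes the combination will produce.

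An exact binomial interval assumes one yes/no outcome per patient. If some patients contribute two events, the percentage is no longer the share of patients who improved, and the interval no longer has its stated coverage. A reader of the study report would naturally take the figure as a share of patients.

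**Working it through.** The documents state no expected conversion rate, so there is no figure to reproduce. The check is on the formula.

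**Set-up.** Among patients with SD or PR at C3D1, let d have two conversions, s have one and u have none, with n = d + s + u. Count upward steps only, so that two is the most a patient can have (SD to PR to CR).

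- Rate as written: (2d + s)/n
- Rate by patient: (d + s)/n
- Difference: d/n, which is zero when d = 0
- The written rate exceeds 100% when 2d + s > d + s + u, that is, when d > u

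**Illustration (assumed counts).** n = 10, d = 2, s = 1, u = 7, with exact (Clopper-Pearson) 95% intervals:

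| Counting | Rate | 95% interval |
|---|---|---|
| As written, (2×2 + 1)/10 | 5/10 = 50% | 18.7% to 81.3% |
| By patient, (2 + 1)/10 | 3/10 = 30% | 6.7% to 65.2% |

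The gap is d/n = 2/10, or 20 percentage points.

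**Above 100% (assumed counts).** n = 12, d = 6, s = 1, u = 5 gives 13/12 = 108.3%, for which no binomial interval exists. By patient it is 7/12 = 58.3% (27.7% to 84.8%).

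**Interval below 100%.** Suppose that each patient has one conversion with probability p1 and two with probability p2. The mean count is m = p1 + 2·p2 and the variance is p1 + 4·p2 − m². For p1 = 0.2 and p2 = 0.1, m = 0.40 and the variance is 0.2 + 0.4 − 0.16 = 0.44, against 0.40 × 0.60 = 0.24 under the binomial. Exact coverage of m by the nominal 95% interval, over a range of assumed probabilities:

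| p1 | p2 | Coverage, n = 12 | Coverage, n = 24 |
|---|---|---|---|
| 0.3 | 0 | 97.7% | 97.7% |
| 0.2 | 0.05 | 93.6% | 93.7% |
| 0.2 | 0.1 | 87.6% | 88.0% |
| 0.2 | 0.2 | 79.4% | 79.7% |
| 0.2 | 0.3 | 67.6% | 70.6% |

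In the last row the chance of a rate above 100% is 17.0% (n = 12) or 10.9% (n = 24). In the first row, with no double conversions, the interval behaves as it should. The fault comes only from repeat counting.

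**A second gap in the numerator.** It is not limited to denominator patients. On the wording alone, CR at C3D1 followed by PR and then CR would add a PR to CR conversion with no matching patient below the line.

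**Groups.** Protocol 9.4.3 names Group 2. SAP Section 10 lists Group 2, CTCL and overall for all efficacy data. SAP 10.5.1 names only overall for this rate. The three do not agree.

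**The case against.** The best defence is that a per-patient proportion was meant all along. The rate is anchored to status at C3D1; the phrase allowing SD to reach either PR or CR can be read as one conversion however far the patient goes; and the binomial interval is the one used for the objective response rate just above. On that reading the interval is valid. This may well be the intention, but the displayed formula does not say so, and a programmer would work from the formula. SAP 10.6.2 writes a once-per-patient rule for adverse events, and 10.5.1 has no counterpart.

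A reader might infer that the rate is bound to be biased, or that it could realistically reach 200%. The documents do not support either. Bias needs repeat conversions. Counting upward steps, 200% would need every denominator patient to have SD at C3D1 and then step up twice. Each double converter must also pass through CR, and the single-agent CR rates in the protocol are modest: 3/35 (9%) for tenalisib, with none among 20 CTCL patients (1.1.2), and 15% in PTCL and 6% in CTCL for romidepsin (1.2). These are not rates for this combination, but they suggest that the upper rows of the coverage table are more plausible than the lower ones.

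A reader might also infer that the CTCL figure will not be produced. That is not established, because SAP Section 10 lists Group 2 and CTCL displays. SAP Section 2 also allows the SAP to modify the protocol. What remains is an inconsistency, with no stated decision to drop the Group 2 figure.

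The stakes are limited. The conversion rate is not a listed endpoint, no hypothesis is tested (SAP 9.1), and the response listings in SAP Section 14 should let a careful reader rebuild the count.

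**Conclusion.** The point holds conditionally. As written, the formula permits a patient to count twice. If any patient does, the rate is overstated by d/n and the exact binomial interval does not apply; if none does, the result is correct. Exceeding 100% is possible only if double converters outnumber non-converters, counting upward steps only. The 50% against 30% example and the coverage figures rest on assumed counts and probabilities, because the documents give none.

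The group issue is a separate inconsistency between Protocol 9.4.3, SAP Section 10 and SAP 10.5.1. This is a descriptive, supportive summary and the primary safety objective is untouched. Even so, a stated formula that can yield a wrong rate and interval should be corrected before the tables are run.

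**What to change.** In SAP 10.5.1, replace the formula's terms:

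- Numerator: number of patients with SD or PR at C3D1 who have at least one improvement (SD to PR or CR, or PR to CR) after C3D1 and up to C8D1, each patient counted once.
- Denominator: number of patients with SD or PR at C3D1.

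This keeps the rate at or below 100%, gives the binomial interval the yes/no outcome it needs, and removes numerator entries from patients outside the denominator.

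In the same paragraph, state that the rate is shown for Group 2 as well as overall, so that it agrees with Protocol 9.4.3 and SAP Section 10.

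The cost is about two lines of SAP text and a small programming change. No new data are needed.
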